8.4.1 Laboratory evaluations

A central laboratory will be used for analysis of all specimens listed below (except for ESR, pregnancy test, Hepatitis B Virus (HBV), Hepatitis B Virus (HCV) and Human immunodeficiency virus (HIV). Details on the collection, shipment of samples and reporting of results by the central laboratory are provided in the laboratory manual. Refer to the Laboratory Manual for identification of laboratory reference range values and the schema for notification of site staff and Novartis for out of range values.

Blood withdrawals and safety assessments should be done prior to study treatment administration and should be taken as shown in Table 8-1.

Laboratory evaluations listed below are to be measured at scheduled visit as indicated in Table 8-1.

| Test Category | Test Name |
|---|--|
| Hematology | Hemoglobin, Red blood cells (RBC), Platelets, White blood cells, Differential (Basophils, Eosinophils, Lymphocytes, Monocytes, Neutrophils including Bands). |
| Chemistry | Albumin (Alb), Alkaline phosphatase (ALP), Alanine Aminotransferase (ALT), Aspartate Aminotransferase (AST), Gamma-glutamyl-transferase (GGT), Lactate dehydrogenase (LDH), Bicarbonate, Calcium, Magnesium, Phosphorus, Chloride, Sodium, Potassium, Creatinine, , Total Bilirubin, Total Protein, Blood Urea Nitrogen (BUN) or Urea, Uric Acid and Glucose. |
| Urinalysis | Macroscopic Panel: pH, Glucose, Protein, Blood, Bilirubin, Urobilinogen, Ketones, , Specific Gravity, White Blood Cells (WBC). A midstream urine sample (approx. 30 mL) will be obtained, in order to avoid contamination with epithelial cells and sediments, and allow proper assessments. Urine sample should be collected and sent to central lab for analysis. If the results are not in the normal ranges, the investigator will evaluate whether further testing is required or not. This testing will be done at the local lab. |
| Lipid panel | High-density Lipoprotein (HDL), Low-density Lipoprotein (LDL), total cholesterol and triglycerides. The lipid panel will be measured from a fasting sample. |
| Autoantibodies | Anti-nuclear antibodies (ANA) and anti-dsDNA will be assessed at the visits/time points indicated in Table 8-1. In addition, RF and anti-CCP must be tested negative for a participant being eligible in this study as per inclusion criteria 5. |

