| Hepatitis markers & HIV (locally, as applicable) | Hepatitis and HIV testing is to be performed at the second Screening visit and the results to be known prior to randomization to determine the participant's eligibility for the trial. Hepatitis testing will include hepatitis B surface antigen (HBsAg) and anti-HCV antibodies. |
| Pregnancy Test (locally) | Serum / Urine pregnancy test for Women of Childbearing Potential (WoCBP). Recommended to perform urine pregnancy test at designated visits in local lab, if not feasible alternatively the serum pregnancy test should be performed. |

Table 8-5Laboratory evaluations

Clinically significant abnormalities must be recorded as either medical history/current medical conditions or adverse events as appropriate. All participants with laboratory tests containing clinically significant abnormal values are to be followed until the values return to normal ranges or until a valid reason, other than treatment related AE, is defined.

Clinically notable lab values are defined in Section 16.1.

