All adverse events must be treated appropriately. Treatment may include one or more of the following:

- No action taken (i.e. further observation only);
- Study treatment temporarily interrupted;
- Study drug(s) permanently discontinued;
- Concomitant medication given;
- Non-drug therapy given.
- 6. Its outcome (not recovered/not resolved; recovered/resolved; recovering/resolving, recovered/resolved with sequelae; fatal; or unknown)

Conditions that were already present at the time of informed consent should be recorded in medical history of the participant.

Adverse events (including lab abnormalities that constitute AEs) should be described using a diagnosis whenever possible, rather than individual underlying signs and symptoms.

Adverse event monitoring should be continued for at least 12 weeks following the last dose of study treatment.

Once an adverse event is detected, it must be followed until its resolution or until it is judged to be permanent (e.g. continuing at the end of the study), and assessment must be made at each visit (or more frequently, if necessary) of any changes in severity, the suspected relationship to the interventions required to treat it, and the outcome.

Information about adverse drug reactions for the investigational drug can be found in the Investigator's Brochure (IB).

Abnormal laboratory values or test results constitute adverse events only if they fulfill at least one of the following criteria:

- they induce clinical signs or symptoms
- they are considered clinically significant
- they require therapy

Clinically significant abnormal laboratory values or test results must be identified through a review of values outside of normal ranges/clinically notable ranges, significant changes from BSL or the previous visit, or values which are considered to be non-typical in participant with the underlying disease. Alert ranges for laboratory and other test abnormalities are included in Section 16.1.

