16.1 Appendix 1: Clinically notable laboratory values and vital signs

The following criteria will be used to define expanded limits and notable abnormalities of key laboratory tests.

| Laboratory variable | Standard units | SI units | | | | |
|---|-----------------------------------|----------------------------|--|--|--|--|
| Liver function and related vari | ables | | | | | |
| Serum Glutamic Oxaloacetic Transaminase (SGOT) (AST) | ≥ 3 × upper limit of normal (ULN) | ≥ 3 × ULN | | | | |
| Serum Glutamic Pyruvic Transaminase (SGPT) (ALT) | ≥ 3 × ULN | ≥ 3 × ULN | | | | |
| Bilirubin | ≥ 2 × ULN | ≥ 2 × ULN | | | | |
| Alkaline phosphatase | ≥ 2 × ULN | ≥ 2 × ULN | | | | |
| GGT | ≥ 2 × ULN | ≥ 2 × ULN | | | | |
| Renal function, metabolic and | electrolyte variables | | | | | |
| Urea | ≥ 5 × ULN | ≥ 5 × ULN | | | | |
| Creatinine | ≥ 3 mg/dL | ≥ 265 µmol/L | | | | |
| Uric acid | M ≥ 12 mg/dL | M ≥ 714 µmol/L | | | | |
| | F≥9 mg/dL | F ≥535 µmol/L | | | | |
| Glucose | < 45 mg/dL | < 2.5 mmol/L | | | | |
| | > 250 mg/dL | > 13.9 mmol/L | | | | |
| Cholesterol | ≥ 350 mg/dL | ≥ 9.1 mmol/L | | | | |
| Triglycerides | ≥ 750 mg/dL | ≥ 8.5 mmol/L | | | | |
| CK (MB) | None | None | | | | |
| Potassium | < or = 3.0 mEq/L | < or = 3 mmol/L | | | | |
| | < or = 6.0 mEq/L | > or = 6 mmol/L | | | | |
| Calcium | < or = 6 mg/dL | < or = 1.5 mmol/L | | | | |
| | > or = 13 mg/dL | > or = 3.2 mmol/L | | | | |
| Magnesium | < 1.0 mg/dL | < 0.4 mmol/L | | | | |
| | > 3.6 mg/dL | > 1.5 mmol/L | | | | |
| Amylase | ≥ 2 x ULN | ≥ 2 x ULN | | | | |
| Lipase | ≥ 2 x ULN | ≥ 2 x ULN | | | | |
| Hematology variables | Hematology variables | | | | | |
| Hemoglobin | < 7 g/dL | < 4.39 mmol/L | | | | |
| Platelets (thrombocytes) | < 50 k/mm ³ | < 50 × 10 ⁹ /L | | | | |
| | ≥ 700 k/mm³ | ≥ 700 × 10 ⁹ /L | | | | |
| Leukocytes (WBCs) | ≤ 2.0 k/mm ³ | ≤ 2.0 × 10 ⁹ /L | | | | |
| | ≥ 16 k/mm³ | ≥ 16 × 10 ⁹ /L | | | | |

| Table 16-1Clinically notable laboratory values and vital signal | jns |
|---|-----|
|---|-----|

| Laboratory variable | Standard units | SI units | | | |
|---|---|--------------------------|--|--|--|
| Liver function and related var | Liver function and related variables | | | | |
| Hematology variables: Differe | ntial | | | | |
| Granulocytes (poly, neutrophils) | ≤ 1,000/mm ³ | ≤ 1 x 10 ⁹ /L | | | |
| Eosinophils | ≥ 12% | ≥ 12% | | | |
| Lymphocytes | ≤ 1,000/mm ³ | ≤ 1 × 10 ⁹ /L | | | |
| Vital sign variables | Notable criteria | | | | |

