Table 2-1 Overview of analysis on some safety endpoints

Analysis period	AEs & SAEs	AEs-SMQ	AEs by severity	study drug related AEs	notables for (vitals/ECG), lab criteria	Risk
Day 1 – Week 16	• crude incidence	• crude incidence	• crude incidence	• crude incidence	• crude incidence	• crude incidence
Entire Treatment	• crude incidence • exp.time adjusted incidence	• exp.time adjusted incidence	• crude incidence	• crude incidence	• crude incidence	• crude incidence • exp.time adjusted incidence

* Exposure-adjusted incidence rates will be done for the following:
At the PSOC for AE and SAE and Level 1 for Risks and SMQ analysis

For the legal requirements of ClinicalTrials.gov and EudraCT, two required tables on treatment emergent adverse events which are not serious adverse events with an incidence greater than 2% and on treatment emergent serious adverse events and SAE suspected to be related to study treatment will be provided by system organ class and preferred term on the safety set population.

If for a same patient, several consecutive AEs (irrespective of study treatment causality, seriousness and severity) occurred with the same SOC and PT:

- a single occurrence will be counted if there is ≤ 1 day gap between the end date of the preceding AE and the start date of the consecutive AE
- more than one occurrence will be counted if there is > 1 day gap between the end date of the preceding AE and the start date of the consecutive AE

For occurrence, the presence of at least one SAE / SAE suspected to be related to study treatment / non SAE has to be checked in a block e.g., among AE's in a ≤ 1 day gap block, if at least one SAE is occurring, then one occurrence is calculated for that SAE.

The number of deaths resulting from SAEs suspected to be related to study treatment and SAEs irrespective of study treatment relationship will be provided by SOC and PT.

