3.1 Primary endpoint(s)

As it is a bridging study for China registration, this study will pursue an estimation strategy rather than formal hypothesis testing of treatment difference.

Analysis of the pooled data of global pivotal studies (CAIN457F2312, CAIN457F2318, CAIN457F2336 and CAIN457F2342) showed an active drug response rate of about 51.4% and a placebo response rate of 23.1% after 16 weeks for ACR20. With 40 participants (1:1 ratio to two arms), there are approximately 86.0% probability to show at least 50% global treatment difference (14.15%) and approximately 96.0% probability to show positive treatment difference.

Table 3-1 shows the probability of success with different observed response rates.

Table 3-1 Probability of Success with Different Observed Response Rates

	Observed Response Rate				Criterion 1		Criterion 2	
	Secukinumab (p_1)	Placebo (p_2)	p_1-p_2	95% CI of (p_1-p_2)	Aimed Treatment Difference	PoS	Aimed Treatment Difference	PoS
Scenario 1	0.464	0.231	0.233	(-0.053, 0.519)	> 0.1415	0.772	> 0	0.922
Scenario 2	0.514	0.231	0.283	(-0.003, 0.569)	> 0.1415	0.860	> 0	0.960
Scenario 3	0.564	0.231	0.333	(0.048, 0.618)	> 0.1415	0.922	> 0	0.981
Scenario 4	0.614	0.231	0.383	(0.101, 0.665)	> 0.1415	0.961	> 0	0.992

4 Change to protocol specified analyses

In the protocol, Table 16-1 Clinically notable laboratory values and vital signs summarizes the criteria that will be used to define expanded limits and notable abnormalities of key laboratory tests. The notable BP levels defined in protocol are considered as severe clinical significance that may require follow-up action and reporting as appropriate. In this SAP we use the criteria as defined in Table 2-4. Therefore, the SAP will list all events that BP is out of normal range for reporting purpose.

5 Appendix

Summary statistics for continuous variables will include N, mean, standard deviation, minimum, lower quartile, median, upper quartile, maximum. Summary statistics for discrete variables will be presented in contingency tables and will include absolute and relative frequencies.

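### Table 16-1 prints the upper potassium limit with the wrong sign in the standard-units column, which leaves that column with no high-potassium limit

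*Protocol*

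**What the plan says.** Table 16-1 in Protocol Section 16.1 lists clinically notable laboratory values in two columns, standard units and SI units. Potassium has two rows. The low row is consistent across the columns: "Potassium | < or = 3.0 mEq/L | < or = 3 mmol/L". The high row reads "< or = 6.0 mEq/L | > or = 6 mmol/L".

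The table has a stated use. Protocol Section 8.4.1 says "Clinically notable lab values are defined in Section 16.1", and Section 10.1.1 says "Alert ranges for laboratory and other test abnormalities are included in Section 16.1". Section 9.1.1 points to it as general guidance when the investigator judges whether a laboratory abnormality requires stopping treatment, and Section 10.2.2 cites it for follow-up of abnormal values. Potassium is in the chemistry panel of Table 8-5.

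In the SAP, Table 2-1 plans crude incidence under a column headed "notables for (vitals/ECG), lab criteria". SAP Section 4 refers to protocol Table 16-1 by name, but it departs from it only for blood pressure: "In this SAP we use the criteria as defined in Table 2-4". The SAP prints no potassium limit of its own.

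**The concern.** The second potassium row should be the upper limit, because the first row already gives the lower one. In the standard-units column, however, both rows point downwards. Taken as printed, that column calls normal potassium values notable and sets no limit for high ones.

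At stake is one safety threshold in the table that the protocol uses to define notable values and alert ranges. A site or programmer working in mEq/L and following the cell literally would flag values that need no attention and miss high ones.

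**Working it through.** **Inputs.** All come from Protocol Table 16-1, plus one unit identity: potassium is monovalent, so 1 mEq/L = 1 mmol/L.

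- Standard units: K ≤ 3.0; K ≤ 6.0
- SI units: K ≤ 3; K ≥ 6

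**Step 1: do the numbers agree?** 6.0 mEq/L × 1 = 6 mmol/L. The number is the same and only the sign differs.

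**Step 2: which sign is right?** Five other analytes have a low and a high row: glucose, calcium, magnesium, platelets and leukocytes. All five use > or ≥ for the high row in both columns. The calcium high row, directly below potassium, reads "> or = 13 mg/dL | > or = 3.2 mmol/L". The SI potassium cell follows this pattern and the standard-units cell does not.

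**Step 3: is the mismatch isolated?** Count the rows with a laboratory limit in both columns, leaving out CK (MB), which has none:

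- Liver: AST, ALT, bilirubin, ALP, GGT = 5
- Renal, metabolic and electrolyte: urea 1, creatinine 1, uric acid 2, glucose 2, cholesterol 1, triglycerides 1, potassium 2, calcium 2, magnesium 2, amylase 1, lipase 1 = 16
- Haematology: haemoglobin 1, platelets 2, leukocytes 2, granulocytes 1, eosinophils 1, lymphocytes 1 = 8

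The total is 5 + 16 + 8 = 29. The direction matches in 28 rows and differs in one, the upper potassium row.

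**Step 4: what does each column flag if read literally?**

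- Standard units: K ≤ 3.0 or K ≤ 6.0, which reduces to K ≤ 6.0
- SI units: K ≤ 3.0 or K ≥ 6.0

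| Potassium | Standard-units column | SI column |
|---|---|---|
| 2.9, 3.0 | notable | notable |
| 3.1, 4.0, 5.0, 5.9 | notable | not notable |
| 6.0 | notable | notable |
| 6.1, 6.5 | not notable | notable |

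The columns agree only at values of 3.0 or below and at exactly 6.0. Between 3.0 and 6.0 only the standard-units column flags, and above 6.0 only the SI column flags.

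**Step 5: is it corrected elsewhere?** SAP Section 4 changes only the blood pressure criteria. The CTCAE list in SAP Section 2.7.3 and Table 2-2 does not include potassium. No other place in either document gives a high-potassium limit.

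**The case against.** The strongest reply is that this is an obvious typing slip and that nothing depends on it. The correct limit stands in the next cell of the same row, and nobody would treat every potassium value up to 6.0 as notable. Protocol Section 8.4.1 states "A central laboratory will be used for analysis of all specimens listed below", with few exceptions, none of them potassium, and refers to the laboratory manual for notification of out-of-range values. Section 10.1.1 has investigators review values outside the normal range as well as the notable range, so a raised potassium would be looked at anyway. Whether it becomes an adverse event or a reason to stop treatment rests mainly on clinical judgment. All of this stands, and it is why the point is minor.

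The link to the SAP is also loose. The laboratory criteria that SAP Section 2.7.3 spells out are CTCAE grades without potassium, lipid categories and liver criteria, and its shift tables use normal ranges. No planned analysis is shown to use the 6.0 limit. Against that, Table 2-1 and the notable-abnormalities row of Table 5-2 refer to laboratory notables in general, so use of the limit cannot be ruled out.

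Finally, the text was extracted from a PDF by a program, and a misread sign cannot be fully excluded. It is unlikely: the SI cell beside it and the calcium row below were read with the correct signs. The source page will settle it.

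None of this makes the printed cell correct.

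**Conclusion.** The point holds. The upper potassium limit in the standard-units column of Table 16-1 has its sign reversed. It is the only one of 29 rows where the two columns disagree in direction, and read literally it leaves that column without a high-potassium limit.

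This is a typographical contradiction with an evident intended value, and its priority is low. It touches one safety threshold and has no bearing on the ACR20 analysis, the sample size or any other efficacy result. The conclusion assumes that the extracted text matches the printed page. Whether the error had any consequence depends on the laboratory alert settings and the notable-value programming, neither of which is given in the documents.

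**What to change.** Change the upper potassium cell in the standard-units column of Table 16-1 to ≥ 6.0 mEq/L, matching the SI cell. Confirm that the central-laboratory alert, and any program that counts notable laboratory values for the final safety analysis, uses ≥ 6.0.

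The edit is one cell plus two quick checks. Under Protocol Section 14.1 any protocol change needs a written amendment with the usual approvals, so the correction is best carried in the next amendment made for other reasons. The SAP already covers the final database lock. If no further amendment is planned, a short clarification to sites and a line in the SAP stating the potassium limit would do the same job.

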16.2 Appendix 2: Liver event and laboratory trigger definitions & follow-up requirements

| Table 16-2 | Liver event and laboratory trigger definitions |
|------------|--|
|------------|--|

| LIVER LABORATORY TRIGGERS | Definition/ threshold |
|---------------------------|---|
| LIVER EVENTS | \cdot 3 x ULN < ALT / AST \leq 5 x ULN |
| | · 1.5 x ULN < TBL ≤ 2 x ULN |
| | \cdot ALT or AST > 5 × ULN |
| | ALP > 2 × ULN (in the absence of known bone pathology) |
| | TBL > 2 × ULN (in the absence of known Gilbert syndrome) |
| | \cdot ALT or AST > 3 × ULN and INR > 1.5 |
| | Potential Hy's Law cases (defined as ALT or AST > 3 × ULN and TBL > 2 × ULN [mainly conjugated fraction] without notable increase in ALP to > 2 × ULN) |
| | Any clinical event of jaundice (or equivalent term) |
| | ALT or AST > 3 × ULN accompanied by (general) malaise, fatigue, abdominal pain, nausea, or vomiting, or rash with eosinophilia |
| | Any adverse event potentially indicative of a liver toxicity* |

*These events cover the following: Hepatic failure, fibrosis and cirrhosis, and other liver damagerelated conditions; the non-infectious hepatitis; the benign, malignant and unspecified liver neoplasms TBL: total bilirubin; ULN: upper limit of normal

| Criteria | Actions required | Follow-up monitoring |
|--------------------------------------|--|---|
| Potential Hy's Law case ^a | Discontinue the study treatment immediately Hospitalize, if clinically appropriate | ALT, AST, TBL, Alb, PT/INR, ALP and GGT until resolution ^c (frequency at investigator discretion) |
| | · Establish causality | |
| | Record the AE and contributing factors (e.g., conmeds, med hx, lab) in the appropriate CRF | |
| ALT or AST > 8 × ULN | Discontinue the study treatment immediately | ALT, AST, TBL, Alb, PT/INR, ALP and GGT until |
| | Hospitalize if clinically appropriate | resolution ^c (frequency at investigator discretion) |
| | · Establish causality | |
| | Record the AE and contributing factors (e.g., conmeds, med hx, lab) in the appropriate CRF | |

 Table 16-3
 Follow up requirements for liver events and laboratory triggers

Novartis Clinical Trial Protocol (Version No. 00)

| Criteria | Actions required | Follow-up monitoring |
|--|--|---|
| > 3 × ULN and INR > 1.5 | Discontinue the study treatment immediately Hospitalize, if clinically appropriate Establish causality Record the AE and contributing factors (e.g. conmeds, med hx, lab) in the appropriate CRF | ALT, AST, TBL, Alb, PT/INR, ALP and GGT until resolution ^c (frequency at investigator discretion) |
| > 5 to ≤ 8 × ULN | Repeat LFT within 48 hours If elevation persists, continue follow-up monitoring If elevation persists for more than 2 weeks, discontinue the study drug Establish causality Record the AE and contributing factors (e.g., conmeds, med hx, lab) in the appropriate CRF | ALT, AST, TBL, Alb, PT/INR, ALP and GGT until resolution ^c (frequency at investigator discretion) |
| > 3 × ULN accompanied by symptoms ^b | Discontinue the study treatment immediately Hospitalize if clinically appropriate Establish causality Record the AE and contributing factors (e.g., conmeds, med hx, lab) in the appropriate CRF | ALT, AST, TBL, Alb, PT/INR, ALP and GGT until resolution ^c (frequency at investigator discretion) |
| > 3 to ≤ 5 × ULN (participant is asymptomatic) | · Repeat LFT within the next week · If elevation is confirmed, initiate close observation of the participant | Investigator discretion Monitor LFT within 1 to 4 weeks |
| ALP (isolated) > 2 × ULN (in the absence of known bone pathology) | Repeat LFT within 48 hours If elevation persists, establish causality Record the AE and contributing factors (e.g., conmeds, med hx, lab) in the appropriate CRF | Investigator discretion Monitor LFT within 1 to 4 weeks or at next visit |
| TBL (isolated) > 2 × ULN (in the absence of known Gilbert syndrome) | Repeat LFT within 48 hours If elevation persists, discontinue the study drug immediately Hospitalize if clinically appropriate | ALT, AST, TBL, Alb, PT/INR, ALP and GGT until resolution ^c (frequency at investigator discretion) |

| Criteria | Actions required | Follow-up monitoring |
|---|---|---|
| | Establish causality Record the AE and contributing factors (e.g., conmeds, med hx, lab) in the appropriate CRF | Test for hemolysis (e.g. reticulocytes, haptoglobin, unconjugated [indirect] bilirubin) |
| > 1.5 to ≤ 2 × ULN (participant is asymptomatic) | Repeat LFT within the next week If elevation is confirmed, initiate close observation of the participant | Investigator discretion Monitor LFT within 1 to 4 weeks or at next visit |
| Jaundice | Discontinue the study treatment immediately Hospitalize the participant Establish causality Record the AE and contributing factors (e.g., conmeds, med hx, lab) in the appropriate CRF | ALT, AST, TBL, Alb, PT/INR, ALP and GGT until resolution ^c (frequency at investigator discretion) |
| Any AE potentially indicative of a liver toxicity* | Consider study treatment interruption or discontinuation Hospitalization if clinically appropriate Establish causality Record the AE and contributing factors (e.g. conmeds, med hx, lab) in the appropriate CRF | Investigator discretion |

*These events cover the following: Hepatic failure, fibrosis and cirrhosis, and other liver damagerelated conditions; the non-infectious hepatitis; the benign, malignant and unspecified liver neoplasms TBL: total bilirubin; ULN: upper limit of normal. ^aElevated ALT/AST > 3 × ULN and TBL > 2 × ULN but without notable increase in ALP to > 2 × ULN ^b(General) malaise, fatigue, abdominal pain, nausea, or vomiting, or rash with eosinophilia ^cResolution is defined as an outcome of one of the following: (1) return to BSL values, (2) stable values at three subsequent monitoring visits at least 2 weeks apart, (3) remain at elevated level after a maximum of 6 months, (4) liver transplantation, and (5) death.*Based on investigator's discretion investigation(s) for contributing factors for the liver event can include: Serology tests, imaging and pathology assessments, hepatologist's consultancy; obtaining more detailed history of symptoms and prior or concurrent diseases, history of concomitant drug use, exclusion of underlying liver disease.*

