6.5.2 Dose interruptions

Study treatment interruption should be avoided with the following exceptions:

Study treatment interruption is only permitted if, in the opinion of the investigator, a participant is deemed to be placed at a significant safety risk unless dosing is temporarily interrupted. In such cases study treatment should be interrupted only during the time that this risk is present and ongoing. Study treatment can be restarted at the next scheduled visit after resolution of the safety risk.

The effect of secukinumab on live vaccines is unknown; therefore live vaccines should not be administered during participation in the study. In case a live vaccine has been administered due to a medical urgency, study treatment should be interrupted for 12 weeks. Any study treatment interruption must be recorded on the corresponding eCRF page.

In all cases the **original visit schedule should be maintained** (no recalculation from the last visit).

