Any PFS for which a defect or malfunction is noticed prior to or during the injection at any of the study visits, must be kept at the site until guidance is received from Novartis on whether it should be returned to Novartis for investigation or discarded. Devices identified as defective should be stored according to local guidelines, until specific instruction is discussed with Novartis personnel. Additionally, from BSL onwards, any noticed defect, malfunction, problem during the injections or product complaints with the PFS should be recorded in the source document and the Use of Device eCRF. Sites should detail the issue, the date, the kit number and the visit number. Site will be asked to record based on their judgment whether the observed issue was primarily related to the device or to the user. Device malfunctions should also be immediately reported to Novartis personnel as a necessary replacement kit may need to be provided.

Administration

Single syringes will be packaged in individual boxes. The boxes containing the PFSs with study treatment solution should be kept at 2 to 8°C (36°F and 46°F) (Do Not Freeze) and protected from light. Prior to administration the boxes containing the PFSs with study treatment solution should be allowed to come to room temperature **unopened** for 15-30 minutes prior to injection.

The injections will be administered into the appropriate site of the body (thighs, arms, abdomen), and each injection should be given at a different injection site to reduce the risk of reaction. Each new injection should be given at least one inch from the previously used site. If participant chooses the abdomen, a 2 inch area around the navel should be avoided. Investigational drug should not be injected into areas where the skin is tender, bruised, red, or hard, or where participant has scars or stretch marks.

Used safety syringes should be disposed immediately after use in a sharps container or according to the local regulatory requirements.

Table 6-3Dose and treatment schedule (BSL to Week 12)

| Investigational / Control Drug (Name and Strength) | Dose | Frequency and/or Regimen |
|---|-----------------------------|-------------------------------------|
| Secukinumab 150 mg s.c (Group 1) | 150 mg (1.0mL PFS) | BSL, Week 1,2,3, 4, 8 and 12 |
| Secukinumab Placebo s.c (Group 2) | 0 mg (1.0mL PFS) | BSL, Week 1, 2, 3, 4, 8 and 12 |

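### Read literally, Table 16-3 sets no fixed stop rule when bilirubin and ALP both exceed 2×ULN and ALT/AST is at or below 5×ULN, although bilirubin alone has one

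*Protocol*

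**What the plan says.** Protocol Section 16.2 works in two steps. Table 16-2 defines liver events. One of them is "TBL > 2 × ULN (in the absence of known Gilbert syndrome"), with no condition on the other liver tests. ALP above 2×ULN is another, unless bone disease explains it.

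Table 16-3 then assigns actions:

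- **Bilirubin row**, criterion "TBL (isolated) > 2 × ULN (in the absence of known Gilbert syndrome"): repeat within 48 hours, then "If elevation persists, discontinue the study drug immediately". It also asks for a haemolysis work-up.
- **ALP row**, also limited to *isolated* elevation: repeat and assess causality, with no stop.
- **Potential Hy's Law row**: immediate stop. Footnote a requires ALT/AST above 3×ULN together with "TBL > 2 × ULN but without notable increase in ALP to > 2 × ULN".
- **ALT/AST above 3 and up to 5×ULN, asymptomatic**: "Repeat LFT within the next week", close observation if confirmed, no stop.
- **ALT/AST above 5 and up to 8×ULN**: "If elevation persists for more than 2 weeks, discontinue the study drug".
- **Immediate-stop rows**: ALT/AST above 8×ULN; ALT/AST above 3×ULN with INR above 1.5; ALT/AST above 3×ULN with listed symptoms; jaundice.
- **Row for adverse events that may signal liver toxicity**: asks the investigator to consider pausing or stopping.

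Two other sections apply outside the table. Section 9.1.1 requires discontinuation once the investigator judges a laboratory abnormality to be a safety risk. Section 10.2.1 asks for follow-up of every Table 16-2 liver event, with treatment decisions left to what is appropriate.

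**The concern.** A table of stopping rules should not become more lenient as more liver tests become abnormal. Here a raised ALP does two things. Through footnote a it takes the participant out of the potential Hy's Law row. Through the word *isolated* it also takes the participant out of the bilirubin row. Nothing else in the table picks the case up with a fixed stop.

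The note under SAP Table 2-3 (Section 2.7.3) gives a reason for the first effect: raised ALP can point to biliary obstruction. The same note warns that cases with raised ALP may still turn out to be severe drug-induced liver injury. Neither statement supports a weaker step than bilirubin alone receives.

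What is at stake is the safety of an individual participant with this mixed pattern. A site that follows the table line by line would find no timed stop.

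**Working it through.** The plan states no figure on this point, so the check is to apply the rows to each pattern and then count the doses concerned.

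**Assumptions.** *Isolated* is read as meaning that the other liver tests are not raised, with ALT/AST at or below 3×ULN and ALP at or below 2×ULN taken as not raised. Some rows lose their parameter label in the extracted text. They are read as ALT/AST or TBL rows, in line with the thresholds in Table 16-2. Every line below has TBL above 2×ULN, no known Gilbert syndrome, INR at or below 1.5, no listed symptoms and no jaundice.

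| ALT/AST (×ULN) | ALP (×ULN) | Laboratory rows that match | Fixed stop |
|---|---|---|---|
| ≤ 3 | ≤ 2 | TBL isolated | If it persists at the 48-hour repeat |
| ≤ 3 | > 2 | None | None |
| > 3 to ≤ 5 | ≤ 2 | Potential Hy's Law; asymptomatic ALT/AST | Immediate |
| > 3 to ≤ 5 | > 2 | Asymptomatic ALT/AST | None |
| > 5 to ≤ 8 | > 2 | ALT/AST > 5 to ≤ 8 | After more than 2 weeks |
| > 8 | > 2 | ALT/AST > 8 | Immediate |

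The second and fourth lines are the gap. For example, ALT/AST 4×, TBL 3× and ALP 3×ULN gives observation only. Lower ALP to 2×ULN or less and the same participant stops at once. From ALT/AST above 5×ULN a stop rule exists again.

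**What closes the gap within the table.** At ALT/AST above 3 and up to 5×ULN, any one of INR above 1.5, a listed symptom or jaundice triggers an immediate stop. At ALT/AST at or below 3×ULN only jaundice does, because the INR and symptom rows both require ALT/AST above 3×ULN.

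**Doses concerned.** Dosing is at "BSL, Week 1,2,3, 4, 8 and 12" (Table 6-3), then every 4 weeks from Week 16 to Week 48 (Table 6-4). Post-baseline chemistry is at Weeks 12, 16, 28, 40, 52 and F60 (Table 8-1), sampled before that day's dose (Section 8.4.1). Doses remaining after a test at Week w = (48 − w)/4:

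- Week 12: (48 − 12)/4 = 9
- Week 16: (48 − 16)/4 = 8
- Week 28: (48 − 28)/4 = 5
- Week 40: (48 − 40)/4 = 2
- Weeks 52 and F60: 0

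For persistent bilirubin elevation alone, the stop falls r + 2 + r days after the sample, where r is the result turnaround. The documents do not give r. For assumed values of 0, 3 and 7 days, the stop falls on day 2, 8 or 16. Each is before the next dose on day 28, so no further dose is given. In the gap the table itself stops none of the 9, 8, 5 or 2 remaining doses.

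**The case against.** The best counter-argument is that *isolated* was only meant to say that the case is not a potential Hy's Law case. Table 16-3 exists to carry out Table 16-2, and Table 16-2 lists TBL above 2×ULN with no exception other than Gilbert syndrome. A reading that leaves two simultaneous liver events with no laboratory row looks like loose wording rather than intent. On that reading the bilirubin row applies and there is no gap.

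This may well be what was intended, but the wording points the other way. The ALP row uses the same word, and ALP above 2×ULN can never be a potential Hy's Law case, so there the word would add nothing. The haemolysis work-up in the bilirubin row also suits a rise in bilirubin by itself.

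The second counter-argument is that other protection exists, and this stands. Sections 9.1.1 and 10.2.1 and the adverse-event row all allow a stop, and Section 9.1.1 requires one once a risk is judged. The Section 10.2.1 repeat panel includes PT/INR, which the scheduled chemistry panel does not, so it can bring the immediate-stop INR row into play when ALT/AST is above 3×ULN. None of these sets a fixed stop for this pattern.

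A reader might infer that Section 6.5.2 makes continued dosing the default, because "Study treatment interruption is only permitted if, in the opinion of the investigator" sees a significant safety risk. The documents do not support that. The section limits temporary interruption, not discontinuation, and Sections 9.1.1 and 10.2.1 continue to apply.

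It is also fair to say that the SAP describes the Week 16 analysis as already done, so an amendment might reach few remaining doses.

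**Conclusion.** The point holds as a minor defect in the fixed rules. Under the literal reading, TBL and ALP both above 2×ULN with ALT/AST at or below 5×ULN has no stop rule in Table 16-3, whereas persistent TBL above 2×ULN alone must stop. This depends on *isolated* meaning that the other liver tests are not raised, and on INR at or below 1.5, no listed symptoms where ALT/AST is above 3×ULN, and no jaundice.

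Two stronger conclusions are not supported. Participants are not left unprotected, because a judgement-based stop remains available. The counts of 9, 8, 5 and 2 doses are upper bounds, not expected exposure: they need the pattern to persist and the investigator not to act.

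The frequency of the pattern cannot be derived from the documents and should be low in 40 participants. The ACR20 analysis is unaffected.

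**What to change.** In Table 16-3, delete *isolated* from the TBL above 2×ULN row and keep the Gilbert exception. Add one sentence saying that when several rows match, the strictest governs.

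Both gap patterns then get the 48-hour repeat and the stop if the rise persists. Potential Hy's Law cases and the other immediate-stop rows keep their immediate stop.

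The cost is a short written amendment with sponsor, IRB/IEC and, where required, health-authority approval (Section 14.1), which can be combined with another amendment. Rarely, a participant would have an earlier repeat test or an earlier stop. No scheduled visit or test is added. Where sites already read *isolated* as excluding only potential Hy's Law cases, the two gap patterns are handled no differently.
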